13.7.1.1 AE Summary for Part 1 of the Study

In Part 1, the blinded, single dose crossover part of the study, AEs will be tabulated by the following periods:

- The double-blinded study treatment period (Lupin Tiotropium Inhalation Powder, SPIRIVA HANDIHALER and Placebo)
- during washout
- during follow-up

Adverse events (AEs) occurring after a study treatment during a treatment day and the day immediately after the treatment will be assigned to the relevant study treatment group. AEs occurring between the treatment days will be assigned to the washout period.

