### **9.3.4 Open-Label Treatment Period (Part 2)**

#### **9.3.4.1 Visit 5 (Day 43)**

Patients participating in the open-label extension will begin study activities on the same day as the final clinic visit in the double-blind treatment period (visit 4, day 43) and will be considered the first day of the open-label extension (visit 5).

The following procedures and assessments will be conducted:

- register/enroll patient in IRT
- demonstration of albuterol/salbutamol MDI and study medication inhaler technique
- dispense ed diary/electronic flow meter

- dispense albuterol/salbutamol MDI, as applicable
- review continuation criteria
- dispense study medication and patient to administer 1st dose in the investigational center under supervision of site personnel (after all visit 4 procedures are completed in Part 1, and patient is enrolled in Part 2)
- check for issues with study inhaler
- review diary/electronic flow meter instructions
- record AEs
- record COPD exacerbations
- record concomitant medications/therapies
- schedule next visit

The patient will be issued with a 90-day supply of Lupin Tiotropium Bromide Inhalation Powder. The daily administration of study medication should be taken at approximately the same time each morning for 72 days.

The patient will also continue using the diary/electronic flow meter throughout Part 2 and asked to measure their lung function (FEV1) twice daily: upon awakening in the morning immediately prior to dosing with the study medication and at 2 (+2) hours after study medication administration. Patients will be asked to record EXACT symptom scores (see [Appendix C](#)) and albuterol/salbutamol MDI/study medication use in their diary.

If at any time patients experience an actual or perceived issue with their inhaler, the diary/IRT system will alert the investigational center who will arrange the necessary corrective action, if required. The investigational center should endeavor to complete the eCRF within 24 hours of notification of an issue.

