9.3 Treatment, Washout and Follow-up

For summary purposes, treatment will be defined as days of dosing and days immediately after dosing, eg, day 0, 1, 21(+3), 22, 42(+3) and 43; washout will be days between treatments; follow-up is defined as 7 ± 3 days after visit 4 for Part 1, for patients who did not enter into the open-label Part 2 extension.

For Part 2, treatment is defined as first dosing date in Part 2 until the end of study or early termination (ET) for Part 2; follow-up is defined as 7 ± 3 days after visit 10.

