9.4 Double-blind Period vs. Open-label Period

The double-blind period is defined as Part 1 of the study, from randomization to visit 4 or early termination before visit 4. For those who do not participate in Part 2 of the study (open-label), it also includes the follow-up period, which is 7 ± 3 days after visit 4.

Open-label period is defined as Part 2 of the study, from enrollment in Part 2 (open-label) to the end of Part 2 study or ET from Part 2. It also includes the follow-up period, which is 7 ± 3 days after visit 10.

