13.7.1.2 AE Summary for Part 2 of the Study

Adverse events (AEs) will be tabulated separately for Part 2 of the study by the following periods:

Sponsor: Lupin Inc.
Protocol no: TB-DPI-301

- The open-label study treatment period, which starts after the first dose of Part 2
- During follow-up

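### For Part 2 entrants, a day-43 adverse event after the open-label dose meets both the Part 1 and the Part 2 assignment rule, and one SAP sentence contradicts the safety-set definition

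*SAP*

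**What the plan says.** **Day 43.** For Part 1 summaries, SAP 9.3 states that "treatment will be defined as days of dosing and days immediately after dosing, eg, day 0, 1, 21(+3), 22, 42(+3) and 43". SAP 13.7.1.1 then allocates AEs: those after dosing on a treatment day and on "the day immediately after the treatment will be assigned to the relevant study treatment group". The groups it lists are the three double-blind treatments. Neither section makes an exception for patients who continue into Part 2.

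The start of Part 2 is described in three ways:

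- SAP 9.3, by date: "For Part 2, treatment is defined as first dosing date in Part 2 until the end of study" or early termination.
- SAP 9.4, by enrollment: "Open-label period is defined as Part 2 of the study, from enrollment in Part 2 (open-label) to the end of Part 2 study" or early termination.
- SAP 13.7.1.2, the section written for AEs, by dose: "The open-label study treatment period, which starts after the first dose of Part 2".

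On the Part 1 side, SAP 9.4 says: "The double-blind period is defined as Part 1 of the study, from randomization to visit 4 or early termination before visit 4". It gives no clock time.

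Protocol 9.3.4.1 has Part 2 entrants "begin study activities on the same day as the final clinic visit in the double-blind treatment period (visit 4, day 43"). The first open-label dose is taken at the center "under supervision of site personnel (after all visit 4 procedures are completed in Part 1, and patient is enrolled in Part 2").

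**Safety set.** SAP 10.3 includes every patient with one or more randomized doses and some data after randomization. SAP 13.7 ties the safety analyses to that definition, and Protocol 11.3.3 agrees with it. In SAP 13.7.1, a sentence says that AEs before randomization are summarized separately and listed. The next sentence says that the patients concerned are outside the safety population. Protocol 11.5.7.1 carries the first of these statements but not the second.

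**The concern.** The safety and tolerability of Test and Reference are the secondary objective, and the Part 1 AE tables are read by comparing treatment columns. An event that starts shortly after active open-label drug should not sit in the placebo or Reference column, and should not be counted in both parts. The rules as written allow both.

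The second defect concerns who is in the tables at all. A patient with an AE during screening or run-in who is later randomized and dosed belongs in the safety set by definition. The sentence in SAP 13.7.1 says otherwise. Protocol 11 gives the SAP precedence in a discrepancy, so the protocol cannot be used to settle it. The SAP has to agree with itself.

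**Working it through.** The plan gives no figure to reproduce. The check is one of logic, with a simple count.

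**Step 1: overlap of the two parts.** The nominal Part 1 treatment days are {0, 1, 21, 22, 42, 43} (SAP 9.3). Part 2 treatment runs from day 43 (visit 5) to day 115 (visit 10). The intersection is {43}. If visit 4 uses its +3-day window, the overlap moves with it and is still one day.

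**Step 2: which rule a day-43 AE meets.**

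| Onset on day 43 | Part 1, period-3 treatment (9.3, 13.7.1.1) | Part 2 by dose (13.7.1.2) | Part 2 by date (9.3) | Part 2 by enrollment (9.4) |
|---|---|---|---|---|
| Before Part 2 enrollment | yes | no | yes | no |
| After enrollment, before the open-label dose | yes | no | yes | yes |
| After the open-label dose | yes | yes | yes | yes |

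The last row is the firm overlap: it arises even under the AE-specific rule of 13.7.1.2. The first two rows overlap only if the date or enrollment wording is used in place of 13.7.1.2.

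The open-label dose comes after all visit 4 procedures, which include the 24-hour spirometry (Protocol 9.3.3.3 and 9.3.4.1). An event in the last row therefore starts about a day or more after the period-3 dose, but soon after open-label active drug.

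**Step 3: which Part 1 column is affected.** The last letter of each sequence in SAP Table 1 gives the period-3 treatment:

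- A (TRP) and F (RTP): placebo
- C (PTR) and E (TPR): Reference
- B (RPT) and D (PRT): Test

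Each treatment is last in 2 of 6 sequences. The number of Part 2 entrants is approximately 120 (SAP 7.2). Assume that the sequences enter Part 2 equally; randomization is 1:1:1:1:1:1, but entry to Part 2 is not randomized.

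- Per treatment: 120 × 2/6 = 40.
- Placebo or Reference last: 40 + 40 = 80, and 80/120 = 66.7%.
- Test last: about 40, for whom the event would appear under Test in Part 1 and again in Part 2.

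To show the sensitivity to unequal entry, with values that are not from the documents: let 30 to 50 entrants have placebo last and hold Reference last at 40. The range is then (30 + 40)/120 = 58.3% to (50 + 40)/120 = 75.0%. These figures count patients for whom misallocation is possible. They do not count events.

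**Step 4: the safety set.** Take a patient with a run-in AE who is then randomized, dosed and followed. Under SAP 10.3 the patient is in. Under the sentence in SAP 13.7.1, read literally, the same patient is out. The documents do not say how many such patients there are.

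**The case against.** The strongest reply on day 43 is that SAP 13.7.1.2 already supplies the cut for AEs. It starts Part 2 after the first open-label dose, and 13.7.1.1 opens by confining itself to Part 1. Read together, events before the dose are Part 1 and events after it are Part 2. Protocol 9.3.4.1 also puts the dose after visit 4 procedures and enrollment, so the periods follow one another.

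Much of this stands, and it limits the point. A reader might infer that every day-43 AE is double counted, or that three incompatible Part 2 starts are in force. The documents do not support that. For AEs, 13.7.1.2 is the specific rule and it leaves events before the dose in Part 1. The wording in 9.3 and 9.4 is more general and needs only to be aligned with it. What the reply does not supply is an end to the Part 1 rule. No sentence stops the next-day attribution in 13.7.1.1 at the open-label dose, and 9.3 names day 43 outright.

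On the safety set, the reply is that 10.3 is the formal definition, 13.7 points to it, and the sentence in 13.7.1 makes sense only for patients who were never dosed. That is probably how it would be applied. A reader might infer that dosed patients will in fact be dropped. That goes too far, because it would mean setting aside both 10.3 and 13.7. The literal contradiction remains, inside the SAP.

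Two further inferences do not hold as errors. Washout AEs are not lost: 13.7.1.1 gives them a category, and column layout belongs to the table shells, which SAP 4.0 places in a separate document. The lack of a default for a missing onset time is absent detail, not a wrong rule.

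**Conclusion.** The point holds in two limited parts.

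(a) For the roughly 120 Part 2 entrants, a day-43 AE that starts after the first open-label dose meets the Part 1 and the Part 2 rule at once. The exposure is the remainder of one day per entrant. For about 80 of 120 (66.7%, assuming equal entry by sequence) the Part 1 column would be placebo or Reference, although the patient had just taken open-label Lupin tiotropium.

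(b) The sentence in SAP 13.7.1 contradicts SAP 10.3 and 13.7 when read literally.

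The number of AEs or patients affected in practice cannot be computed from the documents. A reader might infer that the bioequivalence result is at risk. It is not: the 24-hour spirometry is complete before the open-label dose, and the primary analysis uses the intent-to-treat and per-protocol sets, which are defined separately from the safety set. Only descriptive safety tables are involved. The correction should still be made, because it is cheap and the rules, followed as written, can give wrong counts.

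**What to change.** **(a)** In SAP 9.3, 9.4 and 13.7.1.1, add one rule consistent with 13.7.1.2. Suggested wording: *For patients who enter Part 2, Part 1 AE attribution ends at the date and time of the first open-label dose; an AE with onset at or after that time belongs to Part 2 only.* For AE assignment this replaces the date-based start in 9.3 and the enrollment-based start in 9.4.

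**(b)** In SAP 13.7.1, delete the sentence that puts patients with AEs before randomization outside the safety population, or limit it to screen and randomization failures who were never dosed.

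**Cost.** Wording only, with no new tables; the SAP already provides for a final version before database lock. There are two small drawbacks to (a). The period-3 window becomes slightly shorter for entrants than the windows for periods 1 and 2. The cut also needs a recorded time for the first open-label dose. AE onset date and time are already evaluated (Protocol 10.4) and the dose is supervised at the center (Protocol 9.3.4.1), but the case report form is not among the documents, so recording of the dose time should be confirmed.

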13.7.1.2 AE Summary for Part 2 of the Study

Adverse events (AEs) will be tabulated separately for Part 2 of the study by the following periods:

Sponsor: Lupin Inc.
Protocol no: TB-DPI-301

- The open-label study treatment period, which starts after the first dose of Part 2
- During follow-up

13.7.2 Laboratory Data

Standard clinical laboratory tests including hematology, chemistry, urinalysis and immunochemistry (serum pregnancy) will be performed as indicated in [Table 2](#) Schedule of Events using a central laboratory as indicated in the study procedures manual.

All laboratory data (including re-tests) provided by the central laboratory will be listed.

13.7.3 Vital Signs

Vital signs, including blood pressure, heart rate, respiratory rate and body temperature, will be collected at the screening visit (visit 1) and all subsequent investigational center visits. Descriptive statistics for vital signs at screening and at treatment visits (visits 2 through 4 or ET for Part 1 and visits 7, 9, and 10 or ET for Part 2) will be provided.

For Part 1, the double-blind period, summary statistics will be provided by treatment. Summary statistics will be provided separately for Part 2, the open label extension.

13.7.4 Physical Examinations

For Part 1, physical examination findings at screening (visit 1) and visit 4 or ET will be summarized for any clinically significant findings. Significant changes from screening (visit 1) to the end of the double-blind period will be summarized. Changes from screening (visit 1) to the end of the double-blind period will be presented in 3 by 3 shift tables, where the responses are normal, abnormal but clinically non-significant, or abnormal and clinically significant. Each examination area, eg, skin, abdominal, will have a separate table. Some patients may require 2 PEs before treatment starts. If they do, the first one is the prescreening value and the one at visit 1 is the screening value. Prescreening results will be listed only.

For Part 2 of the study (open-label extension), findings at visit 10 or ET will be summarized for any clinically significant findings and significant changes from screening (visit 1) to the end of the open-label extension using the 3 by 3 shift tables described above.

13.7.5 HEENT, Chest Examination, and Electrocardiograms (ECG)

For Part 1, during the double-blind period, abbreviated physical examination findings (HEENT and chest examinations) will be summarized for any clinically significant findings and significant changes from Visit 2. ECG results will be summarized by visit, and changes in overall clinical interpretation will be summarized.

For Part 2 of the study (open label extension), findings will be summarized for any clinically significant findings and significant changes from Visit 2.

Sponsor: Lupin Inc.
Protocol no: TB-DPI-301

HEENT and chest examination findings will be summarized by four 3 by 3 shift tables where the shift is from visit 2 to each of the 4 visits during treatment, 2 visits in Part 1 and 2 visits in Part 2.

Electrocardiography (ECG) findings will be summarized by four 3 by 3 shift tables where the shift is from screening (visit 1) to each of the 4 visits during treatment, 2 visits in Part 1 and 2 visits in Part 2.

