#### **11.5.7.4 HEENT, Chest Examination, and Electrocardiograms (ECG)**

For Part 1, during the double-blind period, abbreviated physical examination findings (HEENT and chest examinations) and ECG results will be summarized for any clinically significant findings and significant changes from visit 2.

For Part 2 of the study (open label extension), findings will be summarized for any clinically significant findings and significant changes from visit 2.

HEENT and chest examination findings will be summarized by five 3 by 3 shift tables where the shift is from visit 2 to each of the 4 visits during treatment, 2 visits in Part 1 and 2 visits in Part 2.

Electrocardiography (ECG) findings will be summarized by six 3 by 3 shift tables where the shift is from screening (visit 1) to each of the 6 visits during treatment, 3 visits in Part 1 and 3 visits in Part 2.

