13.7 Safety Analyses

Safety analyses will be summarized by treatment for the safety population as defined in [Section 10.3](#) for Part 1 and Part 2 separately. Summary statistics (number of subjects, mean, standard deviation, median, minimum, and maximum) will be included for continuous variables. Summarizations of categorical variables will be presented in tabular form (number of subjects and percentages). Safety of drug regimen will be assessed for adverse events, serious adverse events (SAEs), COPD exacerbations, vital signs, physical examinations, HEENT and chest examinations, ECG recordings, SABA (albuterol/salbutamol MDI) and concomitant medication use.

Listings of all safety measurements will be provided.

Sponsor: Lupin Inc.
Protocol no: TB-DPI-301

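### The SAP plans ECG shift tables for four treatment visits, but its own schedule and the protocol give six, so one of the three Part 2 ECG visits has no shift table

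*SAP*

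**What the plan says.** SAP 13.7.5 specifies four 3 by 3 ECG shift tables, with the shift running "from screening (visit 1) to each of the 4 visits during treatment, 2 visits in Part 1 and 2 visits in Part 2". The sentence just before it gives the same counts for HEENT and chest examinations, but with visit 2 as baseline.

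Protocol 11.5.7.4 uses the same ECG baseline, screening, and plans a shift "to each of the 6 visits during treatment, 3 visits in Part 1 and 3 visits in Part 2".

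The SAP defines treatment in section 9.3. For Part 1, "treatment will be defined as days of dosing and days immediately after dosing", and the examples given include days 0, 21 and 42. For Part 2, "treatment is defined as first dosing date in Part 2 until the end of study or early termination (ET) for Part 2". SAP 13.7.3 lists the treatment visits for vital signs as "visits 2 through 4 or ET for Part 1 and visits 7, 9, and 10 or ET for Part 2". SAP 13.7.4 uses the last visit for the Part 2 physical examination shift tables: "findings at visit 10 or ET will be summarized".

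Protocol section 11 states that the SAP prevails where the two documents differ.

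**The concern.** The ECG sentence repeats the HEENT counts, although the two assessments differ in baseline and in schedule. Followed as written, the SAP leaves one Part 2 ECG visit without the shift table that the protocol plans. A programmer could not tell from the text which of the three Part 2 visits to leave out.

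Part 2 is the part that matters here. Part 1 ECGs are taken before lung function testing and so before that visit's dose (protocol 9.2.2.7 and 9.3.3). Those at visits 3 and 4 also follow a 21-day washout. The ECGs at visits 7, 9 and 10 are the only ones tied to repeated daily dosing, and the early termination visit has no ECG that could stand in.

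**Working it through.** This is a count, so no sample-size or power formula applies.

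**Inputs.** The 12-lead ECG and HEENT rows of SAP Table 2, the treatment definition in SAP 9.3, the shift-table sentences in SAP 13.7.5 and protocol 11.5.7.4, and the visit days in Table 2.

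**Trying to reproduce the stated four**

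| Count | Part 1 visits | Part 2 visits | Total |
|---|---|---|---|
| ECG, screening baseline (as the sentence says) | 2, 3, 4 | 7, 9, 10 | 3 + 3 = 6 |
| ECG, leaving out visit 2 (as baseline or as predose) | 3, 4 | 7, 9, 10 | 2 + 3 = 5 |
| HEENT, visit 2 baseline | 3, 4 | 7, 9 | 2 + 2 = 4 |
| SAP 13.7.5, stated for ECG | not named | not named | 2 + 2 = 4 |
| Protocol 11.5.7.4, stated for ECG | not named | not named | 3 + 3 = 6 |

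Only the HEENT row gives four. Changing the ECG baseline changes the Part 1 count but leaves Part 2 at three.

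**Are all six visits within treatment?** Days 0, 21 and 42 are dosing days and count as treatment in Part 1. Visits 7, 9 and 10 all fall between the first Part 2 dose and the end of the study, so they count as well. SAP 13.7.3 names the same six visits.

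**Coverage under SAP 13.7.5**
- All post-screening ECG visits: 4 of 6.
- ECG visits after a first randomized dose (3, 4, 7, 9, 10): 4 of 5.
- Part 2 ECG visits: 2 of 3.

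**Timing in Part 2**, counted from the first open-label dose on day 43:
- Visit 7: 71 − 43 = 28 days (window 26 to 30).
- Visit 9: 99 − 43 = 56 days (window 54 to 58).
- Visit 10: 115 − 43 = 72 days (window 72 to 75).
- The 72nd daily dose falls on day 43 + 71 = 114.

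If the omitted visit is visit 10, the last ECG with a shift table is at 56 days instead of 72. That it is visit 10 is an inference from the HEENT pattern, since the SAP does not say.

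**The case against.** The strongest reply is that very little is lost. The visit 2 ECG precedes any randomized dose and cannot show a treatment shift, so the real gap is one descriptive table and not two. For Part 2, SAP 13.7.5 also promises that "findings will be summarized for any clinically significant findings and significant changes from Visit 2", without limiting the visits. SAP 13.7 includes ECG recordings among the assessments summarized separately by part, with categorical variables tabulated, and adds that "Listings of all safety measurements will be provided". Clinically significant ECG abnormalities are also recorded as adverse events (protocol 10.4.1.2). The cross-tabulation could be rebuilt from the listings.

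The cut might also be deliberate. Protocol section 11 allows the SAP to change the analyses, and visit 10 nominally falls the day after the 72nd dose. The table shells and the SAP change log are separate documents that were not available here, and either might state a reason.

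Most of this stands as a limit on size. The Part 1 point is accepted, and the finding is of minor consequence for the trial's conclusions. Two things remain. First, none of these provisions supplies the shift from screening at the omitted Part 2 visit. The by-visit ECG summary in SAP 13.7.5 sits in its Part 1 paragraph, and a change to abnormal but not clinically significant is not an adverse event. Second, the day-after-last-dose reading conflicts with SAP 13.7.3, which treats visit 10 as a treatment visit, and with SAP 13.7.4, which uses it for shift tables.

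**Conclusion.** The concern holds. The ECG count in SAP 13.7.5 conflicts with the SAP's own schedule and treatment definition, and departs from the protocol without a stated reason. The documents give six shift tables against four in the SAP. Setting aside the predose visit 2 ECG leaves five against four, with the shortfall in Part 2.

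What goes untabulated is mainly shifts from screening to abnormal but not clinically significant at one of three ECG visits tied to daily dosing. No data are lost, and the bioequivalence and superiority analyses are untouched.

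The count rests on the documents alone. That the HEENT count was carried over, and that visit 10 is the visit omitted, are both inferences. A reason recorded in the shells or change log cannot be excluded.

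**What to change.** Before database lock, rewrite the ECG sentence in SAP 13.7.5 to name the visits: shift tables from screening (visit 1) to visits 3 and 4 in Part 1 and to visits 7, 9 and 10 in Part 2. That makes five tables. Add visit 2 if the protocol's six are to be kept. If only two Part 2 visits are intended, name them and give the reason for departing from protocol 11.5.7.4.

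The cost is one SAP sentence and one or two more table shells, using ECG data already being collected. No new assessment or protocol amendment is needed, and study conduct and the primary analysis do not change. The only downside is one or two more tables in the report.
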